10.3.2 Definition of SAE

If an event is not an AE per definition above, then it cannot be an SAE even if serious conditions are met (eg, hospitalization for signs/symptoms of the disease under study, death due to progression of disease).

An SAE is defined as any untoward medical occurrence that, at any dose:**1. Results in death****Is life-threatening**

The term 'life-threatening' in the definition of 'serious' refers to an event in which the

participant was at risk of death at the time of the event. It does not refer to an event, which hypothetically might have caused death, if it were more severe.

Requires inpatient hospitalization or prolongation of existing hospitalization

In general, hospitalization signifies that the participant has been detained (usually involving at least an overnight stay) at the hospital or emergency ward for observation and/or treatment that would not have been appropriate in the physician's office or outpatient setting. Complications that occur during hospitalization are AEs. If a complication prolongs hospitalization or fulfills any other serious criteria, the event is serious. When in doubt as to whether "hospitalization" occurred or was necessary, the AE should be considered serious. Hospitalization for elective treatment of a pre-existing condition that did not worsen from baseline is not considered an AE.

Results in persistent disability/incapacity

- The term disability means a substantial disruption of a person's ability to conduct normal life functions.
- This definition is not intended to include experiences of relatively minor medical significance such as uncomplicated headache, nausea, vomiting, diarrhea, influenza, and accidental trauma (eg, sprained ankle) which may interfere with or prevent everyday life functions but do not constitute a substantial disruption.

Is a congenital anomaly/birth defect**Other situations:**

- Medical or scientific judgment should be exercised in deciding whether SAE reporting is appropriate in other situations such as important medical events that may not be immediately life-threatening or result in death or hospitalization but may jeopardize the participant or may require medical or surgical intervention to prevent one of the other outcomes listed in the above definition. These events should usually be considered serious.

Examples of such events include invasive or malignant cancers, intensive treatment in an emergency room or at home for allergic bronchospasm, blood dyscrasias or convulsions that do not result in hospitalization, or development of drug dependency or drug abuse.

10.3.3 Recording and Follow-Up of AE and/or SAE**AE and SAE Recording**

- When an AE/SAE occurs, it is the responsibility of the investigator to review all documentation (eg, hospital progress notes, laboratory reports, and diagnostics reports) related to the event.
- The investigator will then record all relevant AE (those AEs leading to dose reduction, interruption/delay and discontinuation and any new Any new CTCAE version 5.0 Grade 3 and 4 AEs, or Grade 2 AEs that affect vital organs [e.g. heart, liver]) and all SAE information in the CRF.
- It is **not** acceptable for the investigator to send photocopies of the participant's medical records to the medical monitor or Bayer's pharmacovigilance department in

lieu of completion of the completed/AE/SAE CRF page.

- There may be instances when copies of medical records for certain cases are requested by the medical monitor or Bayer's pharmacovigilance department. In this case, all participant identifiers, with the exception of the participant number, will be redacted on the copies of the medical records before submission to the medical monitor or Bayer's pharmacovigilance department.
- The investigator will attempt to establish a diagnosis of the event based on signs, symptoms, and/or other clinical information. Whenever possible, the diagnosis (not the individual signs/symptoms) will be documented as the AE/SAE.

Assessment of Intensity

The investigator will make an assessment of intensity for each AE and SAE reported during the study and assign it as per CTCAE Ver 5.0.

Assessment of Causality

- The investigator is obligated to assess the relationship between study intervention and each occurrence of each AE/SAE.
- A "reasonable possibility" of a relationship conveys that there are facts, evidence, and/or arguments to suggest a causal relationship, rather than a relationship cannot be ruled out.
- The investigator will use clinical judgment to determine the relationship.
- Alternative causes, such as underlying disease(s), concomitant therapy, and other risk factors, as well as the temporal relationship of the event to study intervention administration will be considered and investigated.
- The investigator will also consult the Investigator's Brochure (IB) and/or Product Information, for marketed products, in his/her assessment.
- For each AE/SAE, the investigator **must** document in the medical notes that he/she has reviewed the AE/SAE and has provided an assessment of causality.
- There may be situations in which an SAE has occurred and the investigator has minimal information to include in the initial report to Bayer's pharmacovigilance department. However, **it is very important that the investigator always make an assessment of causality for every event before the initial transmission of the SAE data to Bayer's pharmacovigilance department.**
- The investigator may change his/her opinion of causality in light of follow-up information and send an SAE follow-up report with the updated causality assessment.
- The causality assessment is one of the criteria used when determining regulatory reporting requirements.

Follow-up of AEs and SAEs

- The investigator is obligated to perform or arrange for the conduct of supplemental measurements and/or evaluations as medically indicated or as requested by Bayer's pharmacovigilance department to elucidate the nature and/or causality of the AE or SAE as fully as possible. This may include additional laboratory tests or investigations, histopathological examinations, or consultation with other health care professionals.
- If a participant dies during participation in the study or during the safety follow-up period, the investigator will provide the medical monitor and/or Bayer's pharmacovigilance department with a copy of any post-mortem findings including histopathology, if applicable.
- New or updated information will be recorded in the originally completed CRF.
- The investigator will submit any updated SAE data to the Bayer's pharmacovigilance department within 24 hours of receipt of the information.

10.3.4 Reporting of SAEs**SAE Reporting to Bayer's pharmacovigilance department via an Electronic Data Collection Tool**

- The primary mechanism for reporting an SAE to Bayer's pharmacovigilance department will be the electronic data collection tool.
- If the electronic system is unavailable, then the site will use the paper SAE data collection tool (see next section) in order to report the event within 24 hours.
- The site will enter the SAE data into the electronic system as soon as it becomes available.
- After the study is completed at a given site, the electronic data collection tool will be taken off-line to prevent the entry of new data or changes to existing data.
- If a site receives a report of a new SAE from a study participant or receives updated data on a previously reported SAE after the electronic data collection tool has been taken off-line, then the site can report this information on a paper SAE form (see next section).
- Contacts for SAE reporting can be found in the SAE paper template.

SAE Reporting to Bayer's pharmacovigilance department via Paper CRF

- Facsimile transmission of the SAE paper CRF is the preferred method to transmit this information to the Bayer's pharmacovigilance department.
- In rare circumstances and in the absence of facsimile equipment, notification by telephone is acceptable with a copy of the SAE report sent by overnight mail or courier service.
- Initial notification via telephone does not replace the need for the investigator to complete and sign the SAE CRF pages within the designated reporting time frames.

SAE Reporting to Bayer's pharmacovigilance department via Paper CRF

- Contacts for SAE reporting can be found in the SAE paper template.

10.4 Appendix 4: Contraceptive Guidance and Collection of Pregnancy Information

Definitions:

Woman of Childbearing Potential (WOCBP)

A woman is considered fertile following menarche and until becoming post-menopausal unless permanently sterile (see below).

If fertility is unclear (eg, amenorrhea in adolescents or athletes) and a menstrual cycle cannot be confirmed before first dose of study intervention, additional evaluation should be considered.

Women in the following categories are not considered WOCBP

1. Premenarchal
2. Premenopausal female with 1 of the following:
 - Documented hysterectomy
 - Documented bilateral salpingectomy
 - Documented bilateral oophorectomy

For individuals with permanent infertility due to an alternate medical cause other than the above, (eg, mullerian agenesis, androgen insensitivity), investigator discretion should be applied to determining study entry.

Note: Documentation can come from the site personnel's: review of the participant's medical records, medical examination, or medical history interview.

3. Postmenopausal female
 - A postmenopausal state is defined as no menses for 12 months without an alternative medical cause.
 - A high follicle stimulating hormone (FSH) level in the postmenopausal range may be used to confirm a postmenopausal state in women not using hormonal contraception or hormonal replacement therapy (HRT). However, in the absence of 12 months of amenorrhea, confirmation with more than one FSH measurement is required.
 - Females on HRT and whose menopausal status is in doubt will be required to use one of the non-estrogen hormonal highly effective contraception methods if they wish to continue their HRT during the study. Otherwise, they must discontinue HRT to allow confirmation of postmenopausal status before study enrollment.

Collection of Pregnancy Information

Male participants with partners who become pregnant

- The investigator will attempt to collect pregnancy information on any male participant's female partner who becomes pregnant while the male participant is in this study. This applies only to male participants who receive regorafenib.
- After obtaining the necessary signed informed consent from the pregnant female partner directly, the investigator will record pregnancy information on the appropriate

form and submit it to the sponsor within 24 hours of learning of the partner's pregnancy. The female partner will also be followed to determine the outcome of the pregnancy. Information on the status of the mother and child will be forwarded to the sponsor. Generally, the follow-up will be no longer than 6 to 8 weeks following the estimated delivery date. Any termination of the pregnancy will be reported regardless of fetal status (presence or absence of anomalies) or indication for the procedure.

Female Participants who become pregnant

- The investigator will collect pregnancy information on any female participant who becomes pregnant while participating in this study. Information will be recorded on the appropriate form and submitted to the sponsor within 24 hours of learning of a participant's pregnancy.
- The participant will be followed to determine the outcome of the pregnancy. The investigator will collect follow-up information on the participant and the neonate, after obtaining the signed informed consent from both parents of the neonate, unless local law or specific circumstances of the respective case allow otherwise, and the information will be forwarded to the sponsor. Generally, follow-up will not be required for longer than 6 to 8 weeks beyond the estimated delivery date. Any termination of pregnancy will be reported, regardless of fetal status (presence or absence of anomalies) or indication for the procedure.
- While pregnancy itself is not considered to be an AE or SAE, any pregnancy complication or elective termination of a pregnancy will be reported as an AE or SAE. A spontaneous abortion is always considered to be an SAE and will be reported as such. Any post-study pregnancy related SAE considered reasonably related to the study intervention by the investigator will be reported to the sponsor as described in Section 8.3.4. While the investigator is not obligated to actively seek this information in former study participants, he or she may learn of an SAE through spontaneous reporting.

Any female participant who becomes pregnant while participating in the study will discontinue study intervention and will be withdrawn from the study.

10.5 Appendix 5: Abbreviations

AE	Adverse event
ALT	Alanine aminotransferase
AST	Aspartate aminotransferase
AUC	Area under the activity curve
BCRP	Breast cancer resistance protein
BP	blood pressure
CFR	Code of Federal Regulations
CIOMS	Council for International Organizations of Medical Sciences
C _{max}	Maximum observed plasma concentration
CONSORT	Consolidated Standards of Reporting Trials
CRC	Colorectal carcinoma
CRF	Case report form
CTCAE	Common terminology criteria for adverse events
CYP	Cytochrome P450
CYP3A4	Cytochrome P450 3A4
DNA	Deoxy-ribonucleic acid
ECG	electrocardiogram
ECOG	Eastern Cooperative Oncology Group
eCRF	Electronic case report form
e.g.	For example
EoT	End of treatment
FSH	Follicle stimulating hormone
GCP	Good clinical practice
G-CSF	Granulocyte colony-stimulating factor
GIST	Gastrointestinal stroma
GMP	Good Manufacturing Process
HCC	Hepatocellular carcinoma
hCG	Human chorionic gonadotropin
HFSR	hand-foot-skin reaction
HRT	Hormonal replacement therapy
IB	Investigators brochure
IEC	Independent ethics committee
ICF	Informed consent form
ICH	International conference on harmonization
i.e.	id est; that is
IRB	Institutional review board
PI	Principal Investigator
PK	Pharmacokinetics
RCC	Renal cell carcinoma
SAE	Serious adverse event
SoA	Schedule of activities
SUSAR	Suspected unexpected serious adverse reactions
TEAE	Treatment-emergent adverse events
ULN	upper limit of normal
WOCBP	Women of childbearing potential

10.6 Appendix 6 CYP3A4 inducers and inhibitors

Table 10–1 presents an overview of CYP3A4 inducers and **strong** CYP3A4 inhibitors. CYP3A4 inducers and **strong** CYP3A4 inhibitors are NOT allowed due to drug-drug-interaction with regorafenib.

Table 10–1: An overview of CYP3A4 inducers and strong CYP3A4 inhibitors

STRONG CYP3A4 Inhibitors	CYP3A4 Inducers
Boceprevir	Avasimibe
Clarithromycin	Bosentan
Cobicistat, only available in the combination with elvitegravir, emtricitabine, tenofovir or disoproxil fumarate	Carbamazepine
Conivaptan	Efavirenz
Delavirdine	Enzalutamide
Idelalisib	Etravirine
Indinavir	Fosphenytoin
Itraconazole	Hypericum perforatum (St John's Wort)
Ketoconazole	Lersivirine
Lopinavir	Lumacaftor
Mibepradil	Methylphenobarbital
Miconazole	Mitotane
Nefazodone	Modafinil
Nelfinavir	Nafcillin
Posaconazole	Phenobarbital
Ritonavir	Phenytoin
Saquinavir	Primidone
Telaprevir	Rifabutin
Telithromycin	Rifampicin
Tipranavir	Rifamycin
Troleandomycin	Semagacestat
Voriconazole	Thioridazine

The CYP3A4 inducers and strong CYP3A4 inhibitors in Table 10–1 were identified using the Bayer-World Health Organization's Drug Dictionary (WHO-DD) and Bayer drug groupings for CYP3A4 inducers and CYP3A4 inhibitors.

11. References

Not applicable.

7. Document history and changes in the planned statistical analysis	5
8. References	6

Abbreviations

AE	Adverse event
ATC	WHO Anatomical Therapeutic Chemical Classification system
CRF	Case Report Form
ICF	Informed Consent Form
MedDRA	Medical Dictionary for Regulatory Activities
SAE	Serious adverse event
SAP	Statistical Analysis Plan
TEAE	Treatment-emergent adverse event
TESAE	Treatment-emergent serious adverse event

1. Introduction

The primary purpose of the study is to enable participants, currently receiving regorafenib in a Bayer sponsored clinical trial, to continue treatment after their respective study has been completed. A completed study is defined as one that has reached the primary completion endpoint for main data analysis, or has been stopped prematurely, and the respective data have been cleaned. Participants will be able to continue treatment until the treating physician feels the participant is no longer benefiting from treatment.

2. Study Objectives

Primary

• The primary purpose of the program is to enable participants, currently receiving regorafenib in a Bayer sponsored clinical trial and assessed by the principal investigator (PI) to be benefitting, to continue regorafenib treatment after their respective study has met its primary completion date, or main data analysis, or has been stopped prematurely.
Secondary

• Documentation of safety and tolerability

3. Study Design

This is an open label, single arm study.

4. General Statistical Considerations

4.1 General Principles

The statistical evaluation will be performed by using the software package SAS release 9.2 or higher (SAS Institute Inc., Cary, NC, USA). All variables will be analyzed by descriptive statistical methods. The number of data available and missing data, mean, standard deviation, minimum, quartiles, median, and maximum will be calculated for metric data. Frequency tables will be generated for categorical data.

Due to the low number of expected patients no subgroup analyses are planned.

4.2 Handling of Dropouts

All data available will be analyzed.

4.3 Handling of Missing Data

All missing or partial data will be presented in the subject data listing as they are recorded on the Case Report Form (CRF).

The number of subjects who prematurely discontinue the study and study treatment for any reason, as well as the reasons for premature discontinuation of study and study treatment, will be reported.

4.4 Interim Analyses and Data Monitoring

Not applicable

4.5 Data Rules

In general all analyses will be performed for the safety set. It is anticipated that the analysis sets will not differ. Otherwise valuable data which is not available in the safety set will also be analysed. See section 5 for definition of the analysis sets.

4.6 Blind Review

As this is an open label study, no unblinding is necessary. Patients will be assigned to the relevant analysis sets based on the rules described in section 5 for the analysis sets. This will be discussed and documented in the Blind Review Meeting.

5. Analysis Sets

For purposes of statistical analysis, the following analysis sets are defined:

Analysis set	Description
Enrolled	All participants who signed the ICF
Safety	All participants who take at least 1 dose of regorafenib within this rollover study.

5.1 Assignment of analysis sets

Assignment of the subjects to the analysis sets will be made based on the available treatment information (i.e. if there is a record indicating that regorafenib was taken, a patient will be assigned to the safety set).

6. Statistical Methodology

The main objective of the study is to ensure continuation of treatment for eligible patients and only safety data are collected. Beyond summary statistics, no statistical analysis is planned.

6.1 Population characteristics

If applicable, the number of subjects in each analysis set will be presented.

Due to the low number of patients expected in this study, no further summary statistics will be produced. Demographic data will be provided by means of a summary table and individual subject data listings displaying the collected demographic informations as per CRF for all patients enrolled.

6.2 Concomitant medication

Concomitant medication will be analyzed in the safety set.

The frequency of concomitant medications will be summarized by 1st and 3rd level ATC class. This table will be repeated for concomitant anti-cancer therapy, if applicable.

6.3 Study drug exposure

Study drug exposure will be analyzed in the safety set.

Treatment duration will be summarized as well as the number of applications and modifications of the study drug.

6.4 Efficacy

Not applicable

6.5 Pharmacokinetics/pharmacodynamics

Not applicable

6.6 Safety

All analyses will be conducted in the safety set.

AEs will be coded using the latest version of MedDRA during the study. A treatment-emergent adverse event (TEAE) is defined as an AE that increase in severity or that is newly developed after the first study intervention.

If the onset date of an AE is missing/incomplete, it is assumed to have occurred after the first study intervention (i.e., a TEAE) except if the partial onset date or stop date indicates differently.

An overview over all patients experiencing AEs will be given. The total number of patients experiencing TEAEs will be presented and tabulated by SOC and PT and CTCAE grade.

The following categories will be presented:

- TEAEs
- Drug-related TEAEs
- TEAEs leading to discontinuation of study drug
- Treatment-emergent serious adverse events (TESAEs)
- Drug-related TESAEs
- TESAEs leading to discontinuation of study drug

All deaths, TESAEs, TEAEs leading to discontinuation and pregnancies will be presented in subject listings, if applicable.

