1.3 Schedule of Activities (SoA)

Table 1-1: Schedule of activities

Procedure	Screening ^a	Intervention Period ^b [Cycles consisting of 4 weeks]		End of study treatment (up to 14 days after last dose)	Safety Follow-up (30-35 days after last dose, phone call)	Notes
		Cycle 1 Day 1 ^c	Cycle 4 Day 1 + every 3 months (+/- 1 week)			
Informed consent	X					
Inclusion and exclusion criteria	X					Including pregnancy test done by treating physician.
Demography	X					
Tumor type	X					
Medical history	X					Medical important events, e.g. Grade 3/4 (S)AEs, since the start of treatment in the feeder study should be reported as medical history in this rollover study.
Study treatment		→→→→→→→→				Recheck clinical status before 1st dose of study medication. Regorafenib dosing as per feeder study protocol.
Drug dispensing		X	X			
Drug accountability		X	X	X		
AE review	X	X	X	X	X	To be documented only: 
 • AEs leading to dose reduction, interruption/delay and discontinuation • Any ongoing Grade 3 and 4 AEs, or Grade 2 AEs that affect vital organs (e.g. heart, liver) per feeder study protocol CTCAE version. These events need to be regraded by the investigator

						according to CTCAE Ver 5.0. • Any new CTCAE Ver 5.0 Grade 3 and 4 AEs, or Grade 2 AEs that affect vital organs (e.g. heart, liver)
SAE review	X	X	X	X	X	To be documented any ongoing or new SAEs
Concomitant medication review	X	X	X	X	X	

Abbreviations: AE - adverse event; CTCAE - Common terminology criteria for adverse events; SAE - serious adverse event.

a During the screening period the participant will be on treatment under the umbrella of the feeder study. At the end of treatment visit of the feeder study, eligibility criteria will be reviewed and the participants should sign informed consent for the rollover study.

b Safety assessments should be done according to local standard of care and regorafenib label information by the treating physician.

c The treating investigator should ensure a seamless transition without a change in the treatment schedule. Any treatment interruption should not exceed 28 consecutive days including 1 week break.

2. Introduction

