8.3.1 Time Period and Frequency for Collecting AE and SAE Information

All SAEs will be collected from the signing of the informed consent form (ICF until the safety follow-up visit (Section 1.3).

AEs, as described in the SoA, (ie, AEs leading to dose reduction, interruption/delay and discontinuation and any new CTCAE Ver 5.0 Grade 3 and 4 AEs, or Grade 2 AEs that affect vital organs (e.g. heart, liver) will be collected from the signing of the ICF until the safety follow up- visit

Any ongoing Grade 3 and 4 AEs, or Grade 2 AEs that affect vital organs (e.g. heart, liver) per feeder study protocol CTCAE version need to be reported as AEs in this rollover study. These events need to be re-graded by the investigator according to CTCAE Ver 5.0.

Medical important events, e.g. Grade 3/4 (S)AEs, since the start of treatment in the feeder study should be reported as medical history in this rollover study.

Medical occurrences that begin before the start of study intervention but after obtaining informed consent will be recorded on the AE section of the case report form (CRF).

Medical occurrences that started before but deteriorated after obtaining informed consent will be recorded as adverse events.

All SAEs will be recorded and reported to the sponsor or designee immediately and under no circumstance should this exceed 24 hours, as indicated in Appendix 3 (Section 10.3). The investigator will submit any updated SAE data to the sponsor within 24 hours of it being available.

Investigators are not obligated to actively seek AE or SAE after conclusion of the study participation. However, if the investigator learns of any SAE, including a death, at any time after a participant has been discharged from the study, and he/she considers the event to be reasonably related to the study intervention or study participation, the investigator must promptly notify the sponsor.

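### SAP 6.6 counts an ongoing feeder-study event as treatment-emergent when its onset date is missing or cannot be placed before the first rollover dose

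*SAP*

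**What the plan says.** SAP 6.6 (Safety) gives two rules. The first is the definition: a TEAE "is defined as an AE that increase in severity or that is newly developed after the first study intervention". The second covers poor dates: "If the onset date of an AE is missing/incomplete, it is assumed to have occurred after the first study intervention", "except if the partial onset date or stop date indicates differently". All six tabulated AE categories, and the listings of serious events and of events leading to discontinuation, are restricted to treatment-emergent events.

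The protocol determines which events reach these rules. Under 8.3.1, ongoing Grade 3 and 4 events, and Grade 2 events in vital organs, "per feeder study protocol CTCAE version need to be reported as AEs in this rollover study". For these, "These events need to be re-graded by the investigator according to CTCAE Ver 5.0". Collection is otherwise selective. The Schedule of Activities (1.3) opens its AE note with "To be documented only" and lists AEs leading to a dose change or discontinuation, the carried-over events above, and "any new CTCAE Ver 5.0 Grade 3 and 4 AEs, or Grade 2 AEs that affect vital organs". SAEs, ongoing or new, are documented separately. Section 8.3.1 adds: "Medical occurrences that started before but deteriorated after obtaining informed consent will be recorded as adverse events".

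Protocol section 3 lists the frequency and severity of SAEs and protocol-specified AEs as the only endpoint under the primary objectives.

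**The concern.** A default that treats an undated event as treatment-emergent suits a study in which AE collection and study drug start together. Here participants arrive already on regorafenib, and the protocol deliberately puts known feeder-study toxicity into the rollover AE data. For those events the order is not in doubt: the event was present before the first rollover dose. SAP 6.6 nevertheless lets only date information override the default. It makes no use of the fact that the event was recorded as ongoing from the feeder study.

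At stake is whether the TEAE tables, which are the planned safety result, describe what happened on rollover treatment or include older toxicity presented as new.

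A second, smaller point sits in the same paragraph of the SAP. An increase in severity counts as treatment-emergent, but the SAP does not say which grade the increase is measured from.

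**Working it through.** The documents give no TEAE rate or sample size for this point, so there is no figure to reproduce. The check applies the SAP 6.6 rules to each kind of event that Protocol 8.3.1 admits.

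**Carried-over events, ongoing at rollover entry, no later worsening**

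1. Complete onset date before the first rollover dose: neither new nor increased. Not a TEAE. Correct.
2. Partial onset date in an earlier month or year than the first dose: the exception applies. Not a TEAE. Correct.
3. Onset date wholly missing, event still ongoing: there is no partial date and no stop date, so the exception has nothing to work on. Counted as a TEAE. Wrong, because the event is known to be pre-existing.
4. Only the month or year of onset known, and equal to that of the first dose, event still ongoing: the partial date does not place onset before the dose. Counted as a TEAE. Wrong for the same reason.

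In cases 3 and 4 a stop date after the first dose would not help, since it is compatible with onset on either side of that dose.

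**Feeder events below the collection threshold that worsen past it after the first rollover dose**

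5. Entered with the date of worsening as onset: newly developed by date. TEAE. Correct.
6. Entered with the original feeder onset date and no earlier grade: not new by date, and no increase can be shown. Possibly missed.

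Which of 5 and 6 applies depends on the onset-date and grade conventions of the CRF. The SAP cites the CRF, but it is not among the documents. For carried-over events above the threshold, the CTCAE 5.0 re-grading could supply the reference grade, but the SAP does not say that it is the reference.

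**Size**

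If one participant is wrongly counted in a category and has no other event there, the incidence moves by 100 × 1/n percentage points. The protocol (9.2) calls the number of participants unpredictable and the SAP expects it to be low, so n is assumed:

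- n = 5: 100/5 = 20 points
- n = 10: 100/10 = 10 points
- n = 20: 100/20 = 5 points

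These are maxima per participant. If the participant already has another event in the category, the incidence does not move.

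**The case against.** The strongest reply is that treating an undatable event as treatment-emergent is the cautious convention in safety reporting, and that few events will be affected. Entrants must qualify for their next feeder cycle. Any AE that required interruption must have resolved to baseline or be stable (Protocol 5.1). Medically important feeder events are also recorded as medical history. The analysis is descriptive, SAP 4.3 shows partial dates as recorded in the listings, and the overview of patients with AEs and the listing of deaths do not depend on the flag. With few patients, doubtful cases can be inspected one by one.

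Most of this stands as an argument about frequency and consequence. It does not rescue the rule. Caution is a reason for a default when timing is unknown; here it is known from the event's recorded status. Listings let a reader notice the error, but the tables would still carry it.

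Two stronger readings are tempting, and the documents do not support them:

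- A reader might infer that every carried-over event with an incomplete date is counted as new. The SAP's exception prevents that for any date that points to before the first dose.
- A reader might infer that worsening of milder feeder events cannot be recognised, so that counts are wrong in both directions and new eCRF fields are needed. The SAP's definition includes increases in severity. Protocol 8.3.1 has pre-existing conditions that deteriorate after consent recorded as AEs, and Appendix 3 treats exacerbation of a pre-existing condition as an AE. Milder events that are serious or led to a dose change are documented whatever their grade. A loss arises only in case 6, and whether that case can occur turns on the unseen CRF.

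**Conclusion.** The date rule in SAP 6.6 gives a wrong count for a definable set of events: carried-over feeder AEs, still present at rollover entry and not worsening, whose onset is wholly missing or has a partial date that cannot be placed before the first rollover dose. The error adds pre-existing toxicity to the TEAE tables that serve the safety endpoint under the primary objectives. How many events fall in this set is not given and cannot be derived; the 5 to 20 points per participant rest on assumed n between 20 and 5.

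The missing reference grade and the unstated date convention for worsened events are matters for clarification. An under-count there is possible but not established.

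Because the correction is cheap and the affected counts are the planned result, the change should be made, although no hypothesis test depends on it.

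**What to change.** Amend SAP 6.6 before database lock:

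1. Add an exception to the date rule: an AE recorded as ongoing from the feeder study is not treatment-emergent unless it worsens after the first rollover dose, whatever the completeness of its onset date. Alternatively, take the onset date from the feeder data, using the feeder study number and participant number that Protocol 4.1 already has recorded. The second route also serves if the CRF does not mark feeder events directly.
2. Name the CTCAE 5.0 grade at the first rollover dose as the reference for an increase in severity.
3. State that a pre-existing event that worsens after the first rollover dose is classed by the date of worsening.

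The cost is about three sentences in the SAP and a small change to the derivation of the treatment-emergent flag, plus a look-up in the feeder data if that route is chosen. The documents do not establish a need for new eCRF fields. The CRF should be checked to see which onset date and grade sites enter for events that worsen.
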